## 13.4 Monitoring Guidelines for Stage 2 (Early Study Stopping Rules)

A stopping rule is in place to stop the trial in case there are excessive DLTs (Stage 2) as defined by updated posterior probabilities throughout the trial. At the end of the 21-day evaluation period after each cohort of patients is enrolled, new posterior probabilities will be calculated for each dose. The trial will be stopped if the posterior probability that the lowest dose is unacceptably toxic (> 25% of patients) is greater than 80%. (Zohar & Chevret, 2001).

# 14 Conduct of the Study

#### 14.1 Protocol Deviations

The following definitions are from the Masonic Cancer Center's Standard Operating Procedure (SOP) Deviation Reporting:

Major Deviation: A deviation or violation that impacts the risks and benefits of the research; may impact subject safety, affect the integrity of research data and/or affect a subject's willingness to participate in the research. Deviations that place a subject at risk, but do not result in harm are considered to be major deviations.

Minor Deviation: A deviation or violation that does not impact subject safety, compromise the integrity of research data and/or affect a subject's willingness to participate in the research.

Deviations on University of Minnesota participants must be reported to the IRB as detailed in Section 10.3. One exception to the reporting of protocol deviations is

noncompliance with timeframes that are subject to clinical judgement or do not impact subject safety or data integrity. Timeframes indicated throughout this protocol are intended to be targeted timeframes unless "must" is specified.

#### 14.2 Good Clinical Practice

The study will be conducted in accordance with the appropriate regulatory requirement(s). Essential clinical documents will be maintained to demonstrate the validity of the study and the integrity of the data collected. Master files should be established at the beginning of the study, maintained for the duration of the study and retained according to the appropriate regulations.

#### 14.3 Ethical Considerations

The study will be conducted in accordance with ethical principles founded in the Declaration of Helsinki. The IRB will review all appropriate study documentation in order to safeguard the rights, safety and well-being of the patients. The study will only be conducted at sites where IRB approval has been obtained. The protocol, consent, written information given to the patients, safety updates, annual progress reports, and any revisions to these documents will be provided to the IRB by the Investigator.

#### 14.4 Informed Consent

All potential study participants will be given a copy of the IRB-approved consent to review. The Investigator or designee will explain all aspects of the study in lay language and answer all questions regarding the study. If the participant decides to participate in the study, he/she will be asked to sign and date the consent document. Patients who refuse to participate or who withdraw from the study will be treated without prejudice.

# **Appendix I – ECOG Performance Status**

Developed by the Eastern Cooperative Oncology Group, [name], Group Chair.\*

#### GRADE

### **ECOG PERFORMANCE STATUS**

- Fully active, able to carry on all pre-disease performance without restriction
- Restricted in physically strenuous activity but ambulatory and able to carry out work of a light or sedentary nature, e.g., light house work, office work
- 2 Ambulatory and capable of all selfcare but unable to carry out any work activities; up and about more than 50% of waking hours
- Capable of only limited selfcare; confined to bed or chair more than 50% of waking hours
- 4 Completely disabled; cannot carry on any selfcare; totally confined to bed or chair
- 5 Dead

# **Appendix II – Expected Adverse Events for HCW9218**

HCW9128 has not yet been evaluated in human clinical studies. Thus, the expected AEs are based on the published clinical experience with other related immunotherapies, including recombinant human IL-2 (Dutcher et al, 2014), recombinant human IL-15 (rhIL-15) (Conlon et al, 2019; Miller et al, 2018; Conlon et al, 2015), IL-15 mutein/IL15RαSu-Fc complex (ALT-803, nogapendekin alfa inbakicept) (Lafyatis et al, 2020; Mascarenhas et al, 2020; Yap et al, 2020), TGF $\beta$ RII-Fc fusion (AVID200) (Lafyatis et al, 2020; Mascarenhas et al, 2020; Yap et al, 2020), TGF $\beta$ RII-anti-PD-L1 IgG1 fusion (M7824, bintrafusp alfa) (Tan et al, 2021; Khasraw et al, 2021; Kang et al, 2020; Strauss et al, 2020), and anti-TGF- $\beta$  antibody (fresolimumab) (Lacouture et al, 2015; Morris et al, 2014).

All Adverse Events listed in the Table below are defined as "Expected" for the purpose of Expedited Reporting. These AEs should be reported according to Section 10.

CTCAE v5.0 System Organ Class	CTCAE Term	Reported in Subject Receiving:					
(SOC)		IL-2	IL-15	TGF-β antagonist			
Blood and lymphatic system disorders	Anemia	Х	Х	X			
	Disseminated intravascular coagulation	Х					
	Eosinophilia	Х					
	Febrile neutropenia	Х					
	Leukocytosis	Х					
Cardiac Disorders	Atrial fibrillation	Х					
	Atrial flutter	Х					
	Cardiac arrest	Х					
	Chest pain - cardiac	Х	Х				
	Conduction disorder	Х					
	Mobitz type I	Х					
	Mobitz (type) II atrioventricular block	Х					
	Myocardial infarction	Х					
	Myocarditis	Х					
	Palpitations			Х			
	Pericardial effusion	Χ					
	Pericardial tamponade	Χ					
	Pericarditis	Χ					
	Restrictive cardiomyopathy	Χ					
	Supraventricular tachycardia	Χ	Х				
	Sinus bradycardia	Χ					
	Ventricular arrhythmia	Χ					
	Ventricular tachycardia	Χ	Х				
Endocrine disorders Eye disorders	Hypothyroidism	Χ					
	Blurred vision		Х				
	Extraocular muscle paresis			Х			
	Optic nerve disorder	Χ					
	Other, mydriasis	Χ					
	Other, pupillary disorder	Х					
	Papilledema		Х				
	Uveitis		Х				
Gastrointestinal disorders	Abdominal distension	X					

CTCAE v5.0 System Organ Class	CTCAE Term	Reporte	d in Subject F	Receiving:
(SOC)		IL-2	IL-15	TGF-β antagonist
	Abdominal pain	Х	Х	X
	Colitis	Х		
	Colonic perforation	Х		
	Constipation			Х
	Diarrhea	Х	Х	Х
	Duodenal hemorrhage	Х		
	Duodenal ulcer	Х	Х	
	Esophageal fistula	Х		
	Gastritis	Х	Х	
	Lower gastrointestinal hemorrhage	Х		
	Nausea	Х	Х	Х
	Mucositis oral	Х	Х	
	Obstruction gastric	Х		
	Oral hemorrhage			X
	Pancreatitis	Х	Х	
	Rectal perforation	Х		
	Retroperitoneal hemorrhage	Х		
	Small intestinal perforation	Х		
	Intra-abdominal hemorrhage	Х		
	Upper gastrointestinal hemorrhage	Х		
	Visceral arterial ischemia	Х	Х	
	Vomiting	Х	Х	Х
General disorders and administration	Chills	Х	Х	
site conditions	Edema limbs	Х	Х	
	Fatigue	Х	Х	Х
	Fever	Х	Х	X
	Flu like symptoms	Х	Х	Х
	Hypothermia	Х		
	Localized edema	Х		
	Malaise	Х		
	Multi-organ failure	Х		
	Injection site reaction	Х	Х	X
	Pain	Х	Х	
Hepatobiliary disorders	Cholecystitis	Х		
	Hepatic failure	Х		
Immune system disorders	Allergic reaction	Х		
	Anaphylaxis	Х		
	Cytokine release syndrome	Х	Х	
Infections and infestations	Bacteremia	Х	Х	
	Endocarditis infective	Х		
	Hepatic infection	Х		
	Lung infection	Х	Х	
	Meningitis	Х		
	Shingles			X
	Skin infection	Х		
	Sepsis	Х	Х	

CTCAE v5.0 System Organ Class	CTCAE Term	Reporte	d in Subject F	Receiving:
(SOC)		IL-2	IL-15	TGF-β antagonist
Investigations	Alanine aminotransferase increased	Х	Х	
	Alkaline phosphatase increased	Х	Х	
	Aspartate aminotransferase increased	Х	Х	
	Blood bilirubin increased	Х	Х	
	Cardiac troponin I increased		Х	
	CPK increased			Х
	Creatinine increased	Х	Х	
	Lymphocyte count decreased		Х	
	Neutrophil count decreased	Х	Х	
	Platelet count decreased	Х	Х	Χ
	Urine output decreased	Х	Х	
	Weight gain	Х		
	White blood cell decreased	Х	Х	
Metabolism and	Acidosis	Х		
nutrition disorders	Anorexia	Х	Х	
	Hyperglycemia	Х		
	Hyperuricemia	X		X
	Hypoalbuminemia	1.	X	7
	Hypocalcemia	X	X	
	Hypomagnesemia	X		
	Hypophosphatemia		Х	
Musculoskeletal and connective tissue	Arthralgia		X	
disorders	Arthritis	X		
alcordoro	Myositis	X		
	Rhabdomyolysis	X		
Neoplasms benign, malignant	Tumor hemorrhage	^		X
Nervous system disorders	Cognitive disturbance	X		X
Neivous system disorders	Dizziness	X		X
	Edema cerebral	X		, , , , , , , , , , , , , , , , , , ,
	Encephalopathy	X		
	Headache	^	X	X
	Intracranial hemorrhage	X	^	X
	Neuralgia	X		^
	Peripheral motor neuropathy	X		
	Seizure	X		
	Stroke	X		
	Syncope  Transient inchemia attacka	X		
Developed disconducts	Transient ischemic attacks	X		
Psychiatric disorders	Agitation	X		
	Anxiety	X	V	
	Confusion	X	X	
	Delirium	X		
	Depressed level of consciousness	Х		
	Depression	X		
	Insomnia	Х		
	Psychosis	Х		

CTCAE v5.0 System Organ Class	CTCAE Term	Reporte	d in Subject F	Receiving:
(SOC)		IL-2	IL-15	TGF-β antagonist
	Suicidal ideation	Х		
Renal and urinary	Acute kidney injury	Х		
disorders	Chronic kidney disease	Х		
Respiratory, thoracic	Adult respiratory distress syndrome	Х		
and mediastinal	Allergic rhinitis	Х	Х	
disorders	Apnea	Х		
	Cough	Х		
	Dyspnea	Х	Х	
	Epistaxis			X
	Laryngeal hemorrhage	Х		Х
	Pleural effusion		Х	
	Pneumothorax	Х		
	Pulmonary edema	Х		
	Respiratory failure	Х		
	Pharyngeal mucositis	Х		
	Tracheal fistula	Х		
Skin and subcutaneous	Dry skin		Х	
tissue disorders	Erythroderma	Х		
	Hyperkeratosis			X
	Pruritus	Х	Х	Χ
	Other, actinic keratosis			X
	Other, basal cell carcinoma			X
	Other, keratoacanthoma			Х
	Other, lichenoid keratosis			X
	Other, squamous cell carcinoma			Х
	Rash acneiform	Х		
	Rash maculo-papular	Х	Х	Х
	Stevens-Johnson syndrome	Х		
	Urticaria	Х		
Vascular Disorders	Arterial thromboembolism	Х		
	Capillary leak syndrome	Х		
	Hypertension		Х	
	Hypotension	Х	Х	
	Other, mucosal bleeding		Х	X
	Phlebitis	Х		
	Thromboembolic event	Х		
	Vasculitis	Х		

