# 2.2.3 Summary of Clinical Findings

HCW9128 has not yet been evaluated in human clinical studies. The published adverse event (AE) profiles of related immunotherapeutics, including recombinant IL-2, recombinant human IL-15 (rhIL-15), IL-15 mutein/IL-15RαSu-Fc complex (ALT-803, nogapendekin alfa inbakicept), TGFβRII-Fc fusion (AVID200), TGFβRII-anti-PD-L1 IgG1 fusion (M7824, bintrafusp alfa) and anti-TGF- $\beta$  antibody (fresolimumab), are provided in Appendix II. These agents contain protein domains that are similar in structure and/or mechanism-of-action as those of HCW9218. See additional information in the IB.

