# 7.2 Most Common and Most Serious Side Effects Seen In Drugs Similar To HCW9218

HCW9128 has not yet been evaluated in human clinical studies. Thus, the expected AEs are based on the published clinical experience with other related immunotherapies, including recombinant human IL-2, recombinant human IL-15, TGFβRII-Fc fusion and anti-TGF-β antibody.

All adverse events listed in Appendix II are defined as "Expected" for the purpose of event documentation and reporting requirements.

The tables below show the most common and most serious side effects seen in drugs similar to HCW9218. This language matches the treatment consent form.

COMMON, SOME MAY BE SERIOUS In 100 people receiving a drug similar to HCW9218, more than 20 and up to 100 may have:	OCCASSIONAL, SOME MAY BE SERIOUS In 100 people receiving a drug similar to HCW9218, from 4 – 20 people may have:	RARE, AND SERIOUS In 100 people receiving a drug similar to HCW9218, 3 or fewer may have:

 
redness, itching and pain or swelling at the injection site
 
infection, especially when white blood cell count is low
 
anemia, which may require a blood transfusion
 
bruising, bleeding
 
nose-bleed
 
fever, chills, pain
 
flu like symptoms
 
swelling in arms and legs
 
pain in belly
 
pain in joints
 
loss of appetite
 
diarrhea
 
dizziness
 
shortness of breath
 
	
 
chest pain
 
skin rash
 
abnormal eye movement
 
constipation
 
bloating
 
cough
 
headache
 
sores in mouth
 
depression
 
anxiety/ worry
 
extreme sleepiness
 
weight gain
 
abnormal heartbeat
 
blurred vision
 
	
 
skin lesions
 
allergic reaction
 
fluid in the organs
 
heart attack
 
internal bleeding
 
severe blood infection
 
damage to multiple organs, heart, kidney, liver, others
 
swelling, tenderness and/or redness of the veins
 
stroke
 

COMMON, SOME MAY BE SERIOUS In 100 people receiving a drug similar to HCW9218, more than 20 and up to 100 may have:	OCCASSIONAL, SOME MAY BE SERIOUS In 100 people receiving a drug similar to HCW9218, from 4 – 20 people may have:	RARE, AND SERIOUS In 100 people receiving a drug similar to HCW9218, 3 or fewer may have:

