### 10.1 Definitions

The following definitions are based on the Code of Federal Regulations Title 21 Part 312.32 (21CFR312.32(a)).

**Adverse Event:** Any untoward medical occurrence associated with the use of a drug in humans, whether or not considered drug related.

**Suspected Adverse Reaction:** Any adverse event for which there is a reasonable possibility that the drug caused the adverse event.

**Life-Threatening Adverse Event or Life-Threatening Suspected Adverse Reaction:** An adverse event or suspected adverse reaction is considered "life-threatening" if, in the view of either the Investigator or Sponsor, its occurrence places the patient or subject at immediate risk of death. It does not include an adverse event or suspected adverse reaction that, had it occurred in a more severe form, might have caused death.

**Serious Adverse Event or Serious Suspected Adverse Reaction:** An adverse event or suspected adverse reaction is considered "serious" if, in the view of either the Investigator or Sponsor, it results in any of the following outcomes:

- Death
- A life-threatening adverse event
- Inpatient hospitalization or prolongation of existing hospitalization
- A persistent or significant incapacity or substantial disruption of the ability to conduct normal life functions
- A congenital anomaly/birth defect
- An important medical event

Unexpected Adverse Event or Unexpected Suspected Adverse Reaction: An adverse event or suspected adverse reaction is considered "unexpected" if it is not listed in the investigator brochure or is not listed at the specificity or severity that has been observed; or, if an investigator brochure is not required or available, is not consistent with the risk information described in the general investigational plan or elsewhere in the current application, as amended.

Note: An IB for HCW9128 is provided by HCW Biologics.

**Expedited (Rapid) Reporting:** Certain events may require rapid notification to entities providing patient safety oversight (e.g. IRB). Refer to Section 10.3.

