## 10.2 Event Monitoring and Documentation

Event monitoring and documentation begins at the time of the 1st HCW9218 dose and continues through the End of Treatment visit. Active monitoring for adverse events ends with the End of Treatment visit unless there are ongoing study related toxicity. After the EOT through 12 months from Cycle 1 Day 1 (follow-up for response and survival), events are documented upon knowledge. Refer to the table below:

Event	Active Treatment Period		During follow-up for
	Cycle 1 Day 1 through	Cycle 2 Day 1 through	12 months from
	the end of DLT	though End of	Cycle 1 Day 1
	observation period and	Treatment (EOT) visit	(events are
	the DLT assessment is		documented upon
	completed		knowledge)
Any event meeting the definition of serious	X	X	X 1
regardless of attribution or expectedness	^	Λ	^
Any death (date and cause)	Χ	Χ	Χ
1st incidence of a pre-defined adverse event	X 		
during Fast-track enrollment per Section 6.2.1	Λ-		
Any event meeting the definition of a Dose	X3		
Limiting Toxicity (DLT)	Λ'		
All ≥Grade 2 AEs regardless of attribution (see	X	X	
exceptions in Section 10.2.1)	^	^	
Targeted Toxicity Worksheet (Appendix IV) –	X (refer to schedule in		
record all AE grades	Section 10.2.2)		

- 1. Events are documented upon knowledge if they are unexpected and at least possible related to HCW9218.
- 2. Used only once to trigger change from 1 patient cohort to 3 patient cohort and move to Stage 1 Step 2 or Stage 2 (if a DLT also occurs).
- 3. Stage 1: Any event meeting the definition of DLT is in association with the 1st treatment cycle (through the end of the DLT period) is also be reported as a DLT event contributing to subsequent dose cohort decisions per Section 12. Stage 2 (CRM component) event Section 13.4.

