# 10.3 Required Reporting: IRB, HCW Biologics and FDA

Certain events or situations require rapid (expedited) reporting as summarized in the table below as well as reporting to the FDA as a part of the IND annual report.

Agency reporting to	Criteria for reporting	Timeframe	Form to Use	Submit to
U of MN IRB	Unanticipated death of a locally enrolled subject(s); New or increased risk; Any adverse event that requires a change to the protocol or consent form – refer to the IRB website for complete details	5 Business Days	RNI	ETHOS
	Deviations that occur at UMN as defined in Section 14.1	Per current IRB requirements	OnCore Deviation Form and IRB Report Form	
FDA	Unexpected and fatal or unexpected and life threatening suspected adverse reaction  1) Serious, unexpected, and suspected adverse reaction or 2) Increased occurrence of serious suspected adverse reactions over that listed in the investigator brochure or 3) Findings from other sources (other studies, animal or in vitro testing) – not applicable for this study	No later than 7 Calendar Days  No later than 15 Calendar Days	University of Minnesota SAE Report	Submit to FDA as an amendment to IND with a copy to HCW Safety Reporting <[contact]></[contact]>
	All other events per CFR 312.32	At time of annual report	FDA Annual report	Submit to FDA as an amendment to IND
HCW Biologics	Any event meeting the definition of an SAE	Within 24 hours of study team knowledge	University of Minnesota SAE Report	Submit to: HCW Safety Reporting <[contact]></[contact]>

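### Appendix II and Section 10.1 apply different tests of expectedness, so a fatal or life-threatening suspected reaction could miss expedited reporting to FDA

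*Combined protocol and SAP*

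**What the plan says.** Appendix II lists CTCAE terms by organ class, marks each as reported with IL-2, IL-15 or a TGF-β antagonist, and declares: "All Adverse Events listed in the Table below are defined as 'Expected' for the purpose of Expedited Reporting". It adds: "These AEs should be reported according to Section 10". On where the list comes from it says: "Thus, the expected AEs are based on the published clinical experience with other related immunotherapies". Sections 7.2 and 9.7 repeat the declaration and widen its use, making the listed events expected "for the purpose of event documentation and reporting requirements".

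Section 10.1 defines an unexpected event by another reference. An event is unexpected if it is absent from the Investigator's Brochure or "is not listed at the specificity or severity that has been observed". A note there says the supplier provides a Brochure.

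Section 10.3 makes expectedness a condition of FDA expedited reporting. The 7-day report is for an event that is unexpected and is a fatal or "life threatening suspected adverse reaction". The first 15-day criterion requires an event that is serious, unexpected and suspected.

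The documentation table in Section 10.2 has a row for serious events whatever their cause and whether or not expected. For the follow-up period, footnote 1 narrows that row: "Events are documented upon knowledge if they are unexpected and at least possible related to HCW9218".

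**The concern.** The protocol contains two reference standards for one regulatory judgement and does not say which prevails. One is the Brochure, read for severity and specificity. The other is a list of terms from other drugs, with no severity at all. Section 7.1 warns that combining the two activities of HCW9218 may bring events that are more severe than those seen with the comparator agents. A list without grades cannot register that difference.

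What is at stake is how soon FDA hears of a fatal or life-threatening suspected reaction in a trial that Section 11.3 classes as high risk, under a locally sponsored IND. A lesser matter is whether some late serious events enter the trial's record.

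**Working it through.** The plan states no figure on this point. The only arithmetic is a count of the table; the rest is a comparison of the rules.

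**Size of the list.** CTCAE terms in the Appendix II table, in the order of the organ classes (endocrine and eye taken together):

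5 + 18 + 8 + 23 + 11 + 2 + 3 + 8 + 13 + 8 + 4 + 1 + 12 + 9 + 2 + 13 + 13 + 8 = 161 terms, in 19 organ classes.

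Of these, 88 are marked for IL-2 alone: 88/161 = 55%. They include cardiac arrest, myocardial infarction, multi-organ failure, hepatic failure, respiratory failure, stroke and capillary leak syndrome. The table's columns are organ class, term and drug source, with nothing for grade, severity or outcome.

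**One event under both rules.** Take a fatal cardiac arrest during treatment that is suspected to be caused by HCW9218.

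| Step | Appendix II | Section 10.1 |
|---|---|---|
| Reference | The table | The Brochure |
| Severity considered? | Not stated | Yes |
| Classification | Expected, because listed | Expected only if the Brochure lists it at that specificity and severity; otherwise unexpected |
| 7-day FDA report | Condition not met | Required if unexpected |
| First 15-day criterion (serious, unexpected, suspected) | Condition not met | Condition met if unexpected |

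Under the Appendix II column, the remaining 15-day routes are an increased occurrence over the Brochure, and findings from other sources, which Section 10.3 marks as not applicable here. If the increased-occurrence criterion is not met, the event falls to the FDA annual report.

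The Brochure is not among the documents, so there are two cases:

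- The Brochure lists the term at that severity. Both rules then say expected, and there is no divergence for that event.
- The Brochure omits the term or lists it only at lower severity. The rules then disagree, and the difference is a 7-day report against, possibly, the annual report.

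**What does not depend on expectedness.** Under Section 10.3 every SAE goes to the supplier within 24 hours. The IRB hears within 5 business days of an unanticipated death, a new or increased risk, or an event that requires a change to the protocol or consent. Section 10.2 records the date and cause of every death, with no footnote. The DLT definition (Section 6.3) and the Stage 2 stopping rule (Section 13.4) make no use of expectedness.

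**Footnote 1 of Section 10.2.** Because 7.2 and 9.7 apply the Appendix II rule to documentation as well as reporting, a listed event fails the footnote's unexpected condition. Serious events through End of Treatment are recorded in any case, and so are all deaths. What can be lost is therefore a serious, non-fatal, listed event that is possibly related and occurs after End of Treatment.

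**The case against.** The best defence is that the texts can be read together. Appendix II supplies terms and sends the reader to Section 10, and Section 10.1 then applies the severity test. Appendix II never says in terms that fatal events are expected. This reading is possible, but the text does not secure it. Section 10.3 needs a decision on expectedness, and Appendix II has already made that decision, expressly for expedited reporting. The cross-reference sends the reader to a rule whose key input is fixed.

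A second objection is that divergence cannot be shown without the Brochure. That stands as a limit on the size of the effect. A reader might infer that the two rules always give opposite answers. The documents do not support this, because a Brochure that lists the same terms at full severity would bring the answers together. The existence of two standards needs no Brochure to establish.

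A third objection is that safeguards remain, and it too stands. Besides the routes set out above, Section 11.4 plans team safety meetings about every two weeks and Section 11.3 quarterly review by the monitoring council. A reader might infer that a fatal listed event would go unseen, or that listed serious events drop out of the safety data altogether. Neither follows. Even so, none of these routes is an FDA 7-day report.

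The protocol's statement "HCW9128 has not yet been evaluated in human clinical studies" (its spelling of the drug name) may tempt a reader to argue from a total lack of human experience. The revision history for March 2023 reports no DLTs from dose level 1 to dose level 4, so the point does not rest on that statement.

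**Conclusion.** The reporting rules are wrong as written. About 160 ungraded terms drawn from other drugs are classed as expected for expedited reporting, while Section 10.1 requires a test against the Brochure that takes account of severity. Where the Brochure does not list the event at the severity observed, following Appendix II could move an FDA report of a fatal or life-threatening suspected reaction from 7 days to the annual report.

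The conclusion rests on three assumptions: staff apply Appendix II as worded, the Brochure lacks the event at that severity, and the increased-occurrence criterion is not met. How many of the 161 terms satisfy the second condition cannot be determined from the documents. The follow-up gap is narrower, being confined to non-fatal listed serious events after End of Treatment, and in that period events are documented only on knowledge. Determination of the MTD, dose assignment, DLT counting and the stopping rule are unaffected.

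**What to change.** - In Appendix II and Sections 7.2 and 9.7, replace the sentence that defines the listed events as expected. State instead that the table is risk information only and that expectedness is judged solely by Section 10.1, including severity and specificity.
- In footnote 1 of Section 10.2, remove the unexpected condition, so that serious events at least possibly related to HCW9218 are documented on knowledge after End of Treatment. The row label promises documentation whatever the attribution, so it should also say that the follow-up column is limited to related events, if the team keeps that limit.
- Check the Brochure's list, with severities, against the Appendix II terms when the amendment is made, since Section 10.1 then carries the whole decision.

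The cost is a short text amendment, some additional expedited reports and some additional follow-up entries. Sample size, eligibility, dosing and analysis do not change.
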